Data will be transferred in an encrypted PDF format. Trial staff will be given direction on how to share the trial data and given access to one specific section of a controlled cloud service which is controlled via role based access. Once they have authenticated with the service and the service verifies that they have the correct role to access the system they will be directed to a single webpage within the application where they will be able to upload the encrypted PDF. This PDF is generated on the fly and is therefore not stored in another location that could become compromised. Generating the PDF on the fly means that the source data is extracted from the database, processed and delivered in the context of a single request. This is an important factor as this means that after the request finishes the data in the PDF will not be held in application memory once the request is finished and the data relating to the request is freed. After the PDF is generated it is delivered to the assigned statistician using TLS 1.2 (a strong protocol), ECDHE_ECDSA with X25519 (a strong key exchange), and AES_128_GCM (a strong cipher). These data will be transferred for each subject when they complete participation in the study. If they complete the study protocol this will be at the one-year mark, however, if they drop out early then data accrued up until that point will be sent.

References

STATISTICAL CONSIDERATIONS

These statistical considerations were constructed in conjunction with [name] of the bio-statistics unit at the ACTRI.

Randomization

Treatment assignments will be generated via a randomized block procedure, with block sizes randomly chosen in the set {2, 4, 6, 8, 10, 12}. Subjects will be assigned 2:1 between treatment and control groups. Stratification will be performed by gender and center.

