Methods: Primary Aims

For total body weight loss (TBWL) as a continuous measure, we will use a two-sample t-test to examine the differences between the control and active treatment groups at each time period. We will also build one-sided confidence intervals to test whether the difference between groups exceeds a superiority margin of 5%. As a secondary analysis, we will also use a linear regression with TBWL as the dependent variable and group and other covariates of interest (gender, age, etc.) as independent variables. To assess any longitudinal effects, we will use a linear mixed effects model for weight over time, with fixed covariates for baseline weight, time, group, and a time / group interaction, and a random intercept to account for within-subject correlation. We will use a one-sided exact binomial test to determine if the response rate in the treatment group significantly exceeds 35%, with response defined by a loss of at least 5% of their body weight at the 12-month follow-up. We will also use Fisher's exact test to compare the response rates in each group, and, as a secondary analysis, will consider the use of a logistic regression to control for any other covariates of interest. To investigate possible longitudinal trends, we will fit a logistic mixed effects model, similar to the linear mixed effects model described above.

Methods: Secondary Aims

For each continuous and categorical variable at each time point, we will use a two-sample t-test and Fisher's exact test, respectively. Summary statistics (mean, standard deviation, quantiles, counts, and percentages) and plots will be produced for all demographic and study outcomes. We will investigate the effectiveness of the device by usage by including usage time as a continuous covariate in a linear model for TBWL. CTRI Biostatistics Core personnel will conduct all analyses using the latest version of R (R Foundation for Statistical Computing, Vienna, Austria. <http://www.R-project.org/>). No alpha spending function is applied to adjust for multiple comparisons across the secondary aims, and no claims will be made based on any of the secondary endpoints, which are instead viewed as hypothesis generating endpoints.

Missing Data

The primary hypotheses will be tested on the intent-to-treat population. A sensitivity analysis will be

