performed with the binary weight loss endpoint. This analysis will include a best-case scenario (assuming subjects with missing values have all lost over 5% body weight), a worst-case scenario (assuming no subjects with missing values have lost over 5% body weight), and a tipping point analysis (as described in Yan¹). We will check the assumption that the data is missing completely at random, and use multiple imputation techniques to reduce bias in the estimation of the treatment effect. Missing data will be clearly reported and included in tables.

Power Calculation

The primary outcomes are TBWL from the start of treatment until the 12-month mark and the number of subjects who lose at least 5% of their baseline total body weight. We will power both of these tests at the 0.025 significance level (a Bonferroni correction to maintain a family-wise error rate of 0.05 in our primary analysis). For TBWL, we will test the following null and alternative hypothesis:

$$\begin{aligned} H_0: \mu_t - \mu_c &\leq 5\% \\ H_1: \mu_t - \mu_c &> 5\% \end{aligned}$$

where μ_t and μ_c are the treatment and control mean TBWL in the ITT population. We will use a one-sided two-sample t-test to determine if there is a statistically significant difference in TBWL between our control and treatment arms beyond a superiority margin of 5%. With a total sample size of 90 subjects (30 sham and 60 active treatment), this t-test will have 80% power at the $\alpha = 0.025$ significance level to detect an effect size of $d = 0.63$. Assuming a similar standard deviation of TBWL as the ReShape trial (7.5%), this translates to a detectable difference in TBWL between the treatment and control groups of 4.75%. Assuming this same standard deviation, a two-sample superiority test will have 80% power assuming that the true difference between groups is 6.33%.

For the proportion of treatment subjects who lose at least 5% of their baseline total body weight, we will test the following null and alternative hypothesis:

$$\begin{aligned} H_0: P_t &\leq 35\% \\ H_1: P_t &> 35\% \end{aligned}$$

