Subjects will self-administer VeNS or sham stimulation at home for a total of at least 5 hours a week. If they wish the subjects can use the devices for up to 7 hours a week. The devices are able to detect when they are applied properly, as they measure resistance, and they will record usage data, which they will store pending retrieval when the subjects next attend for review. The skin behind the ears will be visually

inspected during follow up visits and all subjects will be provided with aloe vera gel to apply as required, as this is thought to be particularly effective in preventing skin irritation by VeNS. Subjects will also be advised to contact study staff should they have concerns about skin irritation, and will be provided with contact numbers to do so. If they do then a review will be arranged for when next convenient, and the subject will be advised not to use the device until reviewed. If on review there are ongoing concerns about skin irritation, as evinced for instance by redness, then the subject will be withdrawn from the study.

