This then leaves criteria d and g, which both pertain to users suffering significant harm from the device. When the device is turned on it will start at 0mA and the current can then be increased in 0.1mA increments up to 1.0mA. The waveform is a bipolar rectangular shape with 50% duty cycle and – i.e. half the time no current is being delivered. The device is powered via a 4.25V battery and can be recharged

through a USB connection. There is also a hardware interlock to ensure the device cannot be switched on when the charging cable is being used. Please note the device is battery, and not mains, powered.

The devices are placed on the head in a manner analogous to headphones, and the VeNS devices will deliver a small electrical current (1.0mA or less) to the skin behind the ears over the mastoid processes. The device can only be used for up to one hour a day, and after being used for this time period the device will automatically lock out until the next day. Delivery of electrical current to the skin over the mastoid region is known to activate all five components of the vestibular apparatus, but lower level currents (below 3mA) are thought to particularly activate the two otolith organs responsible for detecting linear acceleration and gravity (Zink et al., 1998). It is these otolith organs that, from the animal studies, are particularly associated with a reduction in body fat. This technique – known as bilateral bipolar vestibular stimulation – has been known about since the 19th century and is known to be safe, though skin irritation behind the ears can occasionally occur (Fitzpatrick & Day, 2004).

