More recently Paneri et al. (2015) reviewed the safety of repeated sessions of transcranial electrical stimulation (tES), a term that they use to encompass both the transdermal electrical modulation of cranial nerves (i.e. as in VeNS) and transcranial direct current stimulation (tDCS) of the cerebral cortex. Based on studies of tES on patient groups with depression (Brunoni et al., 2013) and migraine (Magis et al., 2013), and an array of studies of tES on normal volunteers (Brunoni et al., 2011; Kessler et al., 2012; McIntire et al., 2014; Morales-Quezada et al., 2015; Nitsche et al., 2003; Poreisz et al., 2007; Raimundo et al., 2012; Russo et al., 2013; Tadini et al., 2011), together with theoretical assessments of tES (Bikson et al., 2009; Brunoni et al., 2012), they commented that the “safety and tolerability profile previously accumulated regarding extended use of tES in clinical populations is compelling and supports a low-risk or non-significant risk designation” (Paneri et al., 2015).

Paneri et al. (2015) also assessed the safety and tolerability of repeated tES across time in a group of 100 volunteers who were split into three groups. The first group received sham stimulation, the second tES at 2mA, and the third pulses of tES at between 5 to 7 mA (this is notably higher than the 1mA maximum we are proposing to use). A total of 1905 treatment sessions were carried out in total across the three groups. The authors report no serious adverse events in any treatment condition, and that the common side effects were restricted to skin tingling, itching, and mild burning. Moreover, the incidence of these events were not statistically higher in the tES groups (Paneri et al., 2015). These mild skin sensations were not associated with withdrawal from the study and the authors report they became less salient after the first few sessions. Other adverse events, such as headache, were rare (<5%) and statistically indistinguishable across the three groups. Paneri et al. (2015) concluded that the “repeated use of limited output tES across extended periods, is well tolerated and poses no significant risks to healthy subjects, as previously observed in clinical studies”.

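### Ongoing skin irritation removes a subject from the study, not only from the device, so the 12-month weight is probably not taken; this could bias the TBWL difference slightly, in a direction the documents do not settle

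*Combined protocol and SAP*

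**What the plan says.** Device Use Procedure (section 9) first pauses the device until the subject has been reviewed. If concern about irritation persists at review, with redness given as sufficient evidence, "then the subject will be withdrawn from the study". No section describes a subject who stops the device but stays in follow-up.

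Two other places bear on what happens after someone leaves. Data from the Belfast Site says of participants there that "if they drop out early then data accrued up until that point will be sent". Section 20 pays early leavers according to the three-month periods completed, treating departure as the end of involvement.

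On analysis, Missing Data states: "The primary hypotheses will be tested on the intent-to-treat population". Power Calculation defines the TBWL means in that same population. The dose-response item under Secondary Outcome Measures keeps subjects who use the device too little in the main analysis. The sensitivity analysis is to be "performed with the binary weight loss endpoint" and includes a worst case "assuming no subjects with missing values have lost over 5% body weight", a best case and a tipping-point analysis. More generally, the plan will "use multiple imputation techniques to reduce bias in the estimation of the treatment effect", without naming the endpoint or the imputation model. Methods: Primary Aims adds a linear mixed model for weight over time.

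On frequency, Appendix 1 says that "skin irritation behind the ears can occasionally occur". Of a cited tolerability study of repeated transcranial stimulation it reports: "These mild skin sensations were not associated with withdrawal from the study". No withdrawal rate for irritation is given for this trial.

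**The concern.** Intent-to-treat analysis needs the 12-month weight of everyone randomized, whether or not they are still using the device. The rule ties stopping the device to leaving the study, so it creates missing weights that could have been measured. The reason for the loss is a device side effect, and the sham delivers no current (Appendix 1), so the loss may differ by arm.

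It also sits badly with the rest of the plan. A subject who uses the device for two hours a week is kept and analysed. A subject who stops because of irritation is the extreme low user, yet is removed.

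For the binary endpoint, the planned worst-case and tipping-point analyses largely deal with this. For TBWL no missing-data sensitivity analysis is stated. The test is against a 5-point margin, so a shift in the estimated difference feeds directly into the success decision.

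**Working it through.** **The plan's own figures.** Recruitment: 90 / 0.85 = 105.9, rounded up to 106, as stated. TBWL power with 60 active and 30 sham, SD 7.5, a 4.75-point difference tested against zero and one-sided alpha 0.025: the noncentral t gives 80.0%, as stated. The 15% allowance replaces lost numbers; it does not address bias.

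**Inputs from the documents.** SD 7.5 points, margin 5 points, one-sided alpha 0.025, 106 subjects randomized 2:1. That is 106 × 2/3 = 70.7, about 71 active, and about 35 sham.

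**Assumptions.** The number k of active subjects withdrawn for irritation is not given; I take 1, 2 or 3. There is no other loss. Stoppers are omitted or imputed like stayers, and are otherwise exchangeable with them. Each stopper keeps a fraction r of the device effect at 12 months.

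**Formulas.** With true intent-to-treat difference d, the stayers' difference is D = d / (1 − (k/71)(1 − r)), and the excess is D − d. With 71 − k active and 35 sham subjects, SE = 7.5 × √(1/(71 − k) + 1/35), the noncentrality is (D − 5)/SE, and the degrees of freedom are 104 − k. The chance of false success is the probability that this noncentral t exceeds the 97.5% point of the central t.

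Example, d = 5, r = 0, k = 2: D = 5 / (1 − 2/71) = 5.145, excess 0.145. SE = 7.5 × √(1/69 + 1/35) = 1.556. Noncentrality = 0.145/1.556 = 0.093. Error = 0.0309.

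| d | r | k | Excess (points) | One-sided false success |
|---|---|---|---|---|
| 5 | 0 | 1 | 0.071 | 0.0278 |
| 5 | 0 | 2 | 0.145 | 0.0309 |
| 5 | 0 | 3 | 0.221 | 0.0344 |
| 5 | 0.5 | 1 | 0.036 | 0.0264 |
| 5 | 0.5 | 2 | 0.071 | 0.0278 |
| 5 | 0.5 | 3 | 0.108 | 0.0293 |
| 5 | 1 | 1–3 | 0 | 0.025 |
| 4 | 0 | 1–3 | 0.057–0.176 | 0.0052–0.0065 |
| 2 | 0 | 1–3 | 0.029–0.088 | about 0.0001 |

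A simulation of 200,000 trials at d = 5 gave 0.0283, 0.0305 and 0.0345 for r = 0, and 0.0261, 0.0276 and 0.0290 for r = 0.5.

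**The other direction.** Drop the exchangeability assumption. If stoppers would have lost 5 points more than stayers, because they were the most adherent, leaving them out makes the active mean too low by (k/71) × 5 = 0.07, 0.14 or 0.21 points. The 5 points is again only an illustration. This can happen even if the device does nothing, should adherence to the device go with adherence to the diet.

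**Scale.** The full-sample SE is 7.5 × √(1/71 + 1/35) = 1.55 points, so shifts of 0.07 to 0.22 are about 5% to 14% of one standard error.

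**The case against.** No sentence says that a withdrawn subject is not weighed at 12 months. The Belfast text concerns data transfer from one site, and section 20 is a payment clause. This is fair: the missing weight is an inference. It remains the natural reading of withdrawal from the study, and nothing contradicts it.

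A reader might infer that the TBWL difference will be overstated, and that there is no bias if the device has no effect. The documents do not support either statement. Both need stoppers to be otherwise exchangeable with stayers. Subjects are encouraged to raise the current as far as is comfortable and may use the device 5 to 7 hours a week, so those with irritation could be the heaviest users.

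The plan also has real mitigations. The mixed model can use 3- and 6-month weights taken before withdrawal. Adverse-event dropouts and their causes are recorded. Hypoallergenic electrodes, aloe gel and a pause before review should limit the number affected. Appendix 1 reports that in the cited tolerability study skin events were not statistically more frequent than with sham, and both arms here wear electrodes, so some withdrawals would be sham subjects. All of this stands and keeps the point small. It does not supply weights after the device is stopped, which is what imputation or a mixed model would need to represent stoppers properly.

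Finally, the lack of a TBWL sensitivity analysis applies to all dropout, not only to this rule. That is true, and the change proposed here does not fill that wider gap.

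**Conclusion.** The point holds as a minor one. The rule creates avoidable missing 12-month weights for a device-related reason, against the plan's intent-to-treat target and its own treatment of low users. The loss could bias TBWL, and the direction is not settled.

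The size is probably small. The upper figures, an excess of 0.22 points and an error of 0.034, need three active-arm withdrawals, a true difference exactly at the margin, stoppers falling back to the sham mean, no other loss, and omission or stayer-like imputation. Relaxing these generally shrinks the effect: if stoppers keep half the benefit, the error is at most 0.029, and at a true difference of 4 points false success stays below 0.007. The documents do not support reading this as a threat to the trial's validity. The number of withdrawals is an assumption throughout.

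**What to change.** Reword Device Use Procedure so that persistent irritation ends device use only. Unless consent is withdrawn, the subject keeps the scheduled 3-, 6- and 12-month visits, at least for weight, and is analysed in the randomized arm with those data. The clinical criterion for stopping the device, the sample size and the visit calendar are unchanged.

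The cost is a short protocol and consent amendment. Some subjects will decline to return, so the change reduces the missing data but does not eliminate it.

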Appendix 1: Study Devices and Risk Assessment

Background

The VeNS stimulators and sham stimulation devices that will be utilized are being provided free of charge by the company Neurovalens. The sham devices will externally appear identical to the VeNS stimulators, however, they will not deliver an actual electrical current to the skin behind the ears and as such the vestibular nerve will not be stimulated.

Risk Assessment

In terms of this amendment the following risk assessment was also carried out for vestibular nerve stimulation devices that can deliver up to 1mA. Under the guidance for IRBs from the FDA a device will be determined to be non-significant risk (NSR) if it does not meet the definition of a significant risk (SR) device (see <https://irb.ucsd.edu/device.pdf>). A SR device is one which meets at least one of the following criteria:

- a. The device is intended as an implant.
- b. The device supports or sustains human life.
- c. The use of the device is of substantial importance in diagnosing, curing, mitigating, or treating disease, or preventing impairment of health.
- d. The device could cause significant harm to any subjects.
- e. The subject must undergo a procedure as part of the device study.
- f. The device appears on the FDA list of significant risk devices.
- g. The study or any of the study procedures could cause harm to the subjects which:
 - i. could be life threatening;
 - ii. could cause permanent impairment of a body function;
 - iii. could cause permanent damage to body structure;
 - iv. or could necessitate medical or surgical intervention to preclude permanent impairment of a body function or preclude permanent damage to body structure.

As the device is not implanted, no procedure is required to use it, it does not support or sustain life and it is not on the FDA list of significant risk devices, criteria a, b, e and f clearly do not apply. Regarding criterion c, the aim of this study is to investigate whether vestibular stimulation can, in conjunction with lifestyle interventions, assist with fat loss. It may be the case that VeNS has such a role, but it is unlikely that this will be of "substantial importance in ... curing, mitigating, or treating disease, or preventing impairment of health." Thus criterion c does not apply.

This then leaves criteria d and g, which both pertain to users suffering significant harm from the device. When the device is turned on it will start at 0mA and the current can then be increased in 0.1mA increments up to 1.0mA. The waveform is a bipolar rectangular shape with 50% duty cycle and – i.e. half the time no current is being delivered. The device is powered via a 4.25V battery and can be recharged

through a USB connection. There is also a hardware interlock to ensure the device cannot be switched on when the charging cable is being used. Please note the device is battery, and not mains, powered.

The devices are placed on the head in a manner analogous to headphones, and the VeNS devices will deliver a small electrical current (1.0mA or less) to the skin behind the ears over the mastoid processes. The device can only be used for up to one hour a day, and after being used for this time period the device will automatically lock out until the next day. Delivery of electrical current to the skin over the mastoid region is known to activate all five components of the vestibular apparatus, but lower level currents (below 3mA) are thought to particularly activate the two otolith organs responsible for detecting linear acceleration and gravity (Zink et al., 1998). It is these otolith organs that, from the animal studies, are particularly associated with a reduction in body fat. This technique – known as bilateral bipolar vestibular stimulation – has been known about since the 19th century and is known to be safe, though skin irritation behind the ears can occasionally occur (Fitzpatrick & Day, 2004).

More recently Paneri et al. (2015) reviewed the safety of repeated sessions of transcranial electrical stimulation (tES), a term that they use to encompass both the transdermal electrical modulation of cranial nerves (i.e. as in VeNS) and transcranial direct current stimulation (tDCS) of the cerebral cortex. Based on studies of tES on patient groups with depression (Brunoni et al., 2013) and migraine (Magis et al., 2013), and an array of studies of tES on normal volunteers (Brunoni et al., 2011; Kessler et al., 2012; McIntire et al., 2014; Morales-Quezada et al., 2015; Nitsche et al., 2003; Poreisz et al., 2007; Raimundo et al., 2012; Russo et al., 2013; Tadini et al., 2011), together with theoretical assessments of tES (Bikson et al., 2009; Brunoni et al., 2012), they commented that the “safety and tolerability profile previously accumulated regarding extended use of tES in clinical populations is compelling and supports a low-risk or non-significant risk designation” (Paneri et al., 2015).

Paneri et al. (2015) also assessed the safety and tolerability of repeated tES across time in a group of 100 volunteers who were split into three groups. The first group received sham stimulation, the second tES at 2mA, and the third pulses of tES at between 5 to 7 mA (this is notably higher than the 1mA maximum we are proposing to use). A total of 1905 treatment sessions were carried out in total across the three groups. The authors report no serious adverse events in any treatment condition, and that the common side effects were restricted to skin tingling, itching, and mild burning. Moreover, the incidence of these events were not statistically higher in the tES groups (Paneri et al., 2015). These mild skin sensations were not associated with withdrawal from the study and the authors report they became less salient after the first few sessions. Other adverse events, such as headache, were rare (<5%) and statistically indistinguishable across the three groups. Paneri et al. (2015) concluded that the “repeated use of limited output tES across extended periods, is well tolerated and poses no significant risks to healthy subjects, as previously observed in clinical studies”.

This conclusion is in keeping with the findings of Wilkinson et al. (2009), who reported on a stroke patient who received repeated VeNS sessions as part of his rehabilitation therapy. The authors observed no adverse events during stimulation over 5 consecutive daily sessions of VeNS at 1mA for 30 minutes per day. Utz et al. (2011) studied the adverse effects of 255 VeNS sessions at 1.5mA (again higher than the 1mA we propose to use) in 55 stroke patients and 30 healthy controls. They found only a few mild adverse effects, with the most common being slight itching (mean 10.2%) and tingling (mean 10.7%) underneath the electrodes. They concluded that VeNS induces “very few and mild adverse effects in healthy and persons with stroke and [is] safe” (Utz et al., 2011). There is thus a body of literature supporting the safe usage of both tES and specifically VeNS devices delivering at least 1mA in stimulation.

Similarly, in February 2016, Halo Neuroscience, a company based in San Francisco, released additional data on the safety of tES; on this occasion for a 2mA tDCS device used on 1010 subjects.¹ They state that "there were zero reports of burn or seizure activity across all 1010 subjects, zero serious or unexpected adverse effects and zero withdrawals due to adverse events other than unpleasant sensation". They conclude that their tES study showed "a favorable safety profile and [was] associated with a very low incidence of adverse events, with no unexpected or serious adverse events".

Specific measures taken to reduce the incidence of skin irritation are the 32mm diameter of the electrodes, which are themselves hypo-allergenic, and the 50% duty cycle (i.e. half the time no current at all is being delivered), and the maximum current of 1.0mA. This means that the maximum phase current that can be delivered is only 500 μ C. In conclusion, there is not a significant risk of harm from using the device, and as such criteria d and g do not apply. Thus as the device does not meet the criteria of a SR device it is a NSR device.

References

